2.8.3 SF-12

The SF-12 questionnaire is a well-validated self-administered survey derived from the SF-36 questionnaire, consisting of 12 items, used to assess participants' health-related quality of life (HRQoL) over the past four weeks (Ware et al., 1996). The scale originates from the Medical Outcomes Study, a long-term follow-up study of patients with chronic diseases (Goldfarb & Casillas, 2016). The SF-12 primarily covers eight dimensions of physical and mental health and can further calculate two composite indices: the Physical Component Summary (PCS) and the Mental Component Summary (MCS). Each dimension uses a different scoring method, with final scores standardized on a scale of 0 to 100, Scores >50 are above average, where higher scores indicate better health status (Suonpera et al., 2024). Studies conducted in the United States and the United Kingdom on different populations have shown that the Cronbach's α values are all greater than 0.70 (Lin, 2017). Additionally, the SF-12 has been proven effective for assessing the quality of life of patients undergoing coronary artery bypass grafting (CABG). According to the findings of Pačarić et al. (2020), the SF-12 is suitable for measuring the health status of CABG patients.

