2.1 Study Design

A randomized controlled trial (RCT) was conducted in a teaching hospital in northern Taiwan using a two-parallel-group design. Participants were recruited postoperatively and randomly assigned to either the experimental or control group before hospital discharge. Following discharge, the experimental group received a 4-week telehealth care intervention, whereas the control group received standard care only.

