2.7 The intervention group

In addition to standard care, starting from the day of discharge from the hospital, patients in the intervention group were scheduled for telephone interviews every three days, conducted by nine well-trained telenursing specialists. Each interview lasted approximately 10 to 15 minutes, for four weeks. The objective of these telephone interviews was to encourage and monitor the patients' adherence to effective self-health management practices, which included: (1) assessing daily blood pressure, weight, blood glucose levels, and lower

limb edema; (2) providing counseling on medication adherence, physical activity, and dietary hygiene; (3) offering guidance on wound care; (4) advising on the avoidance of cardiovascular risk factors, including smoking and exposure to secondhand smoke, as well as facilitating referrals to appropriate outpatient services, such as nutrition or rehabilitation clinics, based on individual needs. Additionally, patients were provided with a portable electrocardiogram device (ecg103, Quanta Computer Inc, Taipei, Taiwan).

During hospitalization, the research team assisted in installing the ECG software on the patient's mobile device and provided demonstrations until the patient was proficient in independently operating the device. A detailed operation manual was provided, which instructed the patient to measure ECG once in the morning and once in the evening. Patients were instructed to upload ECG data immediately if experiencing chest discomfort. The patient was provided with the website and operating procedures of the telehealth platform. The patient was also instructed to input daily physiological data, including blood pressure and blood glucose levels. Should any abnormalities in heart rhythms, blood pressure, or glucose levels be detected, the researcher contacted with the patient to assess their clinical condition and provide 24-hour online counseling.

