2.8 Data collection

Outcomes were evaluated at three time points: two days before discharge (baseline, T0), at the first outpatient visit (7–10 days post-discharge, T1), and at the end of the intervention (4 weeks post-discharge, T2).

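### If the SF-12's four-week recall is read literally, 18 to 21 of the 28 days covered at T1 precede the intervention, so the SF-12 comparison should rest on T2, adjusted for T0

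*Combined protocol and SAP*

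**What the plan says.** Section 2.8.3 (SF-12) describes the instrument as assessing "health-related quality of life (HRQoL) over the past four weeks", summarised as PCS and MCS. It names no version with a shorter recall period and does not give the item wording.

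Section 2.8 sets three assessments. The starting score is taken "two days before discharge (baseline, T0". The interim assessment takes place "at the first outpatient visit (7–10 days post-discharge, T1". The last one is held "at the end of the intervention (4 weeks post-discharge, T2".

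Section 2.1 places the programme after the hospital stay: "Following discharge, the experimental group received a 4-week telehealth care intervention". Section 2.7 has it "starting from the day of discharge from the hospital", with patients "scheduled for telephone interviews every three days". One element comes earlier: "During hospitalization, the research team assisted in installing the ECG software".

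Section 2.9 lists an independent t-test between groups without naming a visit, a paired t-test within each group from before to after the intervention, and a GEE for change over the time points. It gives no model terms and says nothing about recall. The available text breaks off while naming the software version, so this covers only what can be read.

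**The concern.** A score that looks back four weeks, taken 7 to 10 days after the intervention starts, describes mostly time before the intervention. Both randomised arms share that earlier time, apart from the in-hospital device set-up in the experimental arm. If patients answer for the stated period, the shared days shrink the difference between arms at T1. T2 does not have this problem.

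What is at stake is interpretation. A null SF-12 result at T1 could be read as showing no early effect when the measurement could hardly show one. Because the between-group t-test has no named visit, a diluted T1 comparison could also be reported on the same footing as T2.

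**Working it through.** **The plan's own figure.** Section 2.5 uses an effect size of 0.50, alpha 0.05 and power 0.80. A two-sided two-sample t-test needs 63.77 per arm, rounded up to 64, or 128 in total. Allowing for 20% attrition, 128 / (1 − 0.20) = 160. Both figures reproduce, and the sample size is not in dispute.

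**Recall days before the intervention.** Take discharge as day 0 and the window as 28 days. Days before discharge = max(0, 28 − days since discharge), for visits after discharge.

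| Visit | Day | Recalled days before discharge |
|---|---|---|
| T1, earliest | 7 | 28 − 7 = 21 (75%) |
| T1, latest | 10 | 28 − 10 = 18 (64%) |
| T2 | 28 | 28 − 28 = 0 |

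All of the T0 window precedes discharge, as a baseline should. Section 2.8 gives no window around T2; if T2 fell a day early, one recalled day would precede discharge.

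**Context only.** The Introduction gives an average discharge on day 7 after surgery, as background rather than as this trial's length of stay. On that figure the recalled days before the operation are 28 − 5 = 23 at T0, 28 − 14 = 14 to 28 − 17 = 11 at T1, and none at T2 (35 days after surgery).

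**Early exposure.** Calls every three days from day 0 fall on days 0, 3, 6, 9, …, 27. That is 3 by day 7, 4 by day 10 and 10 by day 28.

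**What dilution could mean at T1 (illustration).** Assume that d = 0.50 applies to the SF-12 with full effect from discharge, and that a share w of the answer reflects post-discharge days. Then d at T1 = 0.50 × w. Power is from the noncentral t, two-sided 0.05, 64 per arm, with noncentrality d × √(64/2).

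| w | d | Noncentrality | Power |
|---|---|---|---|
| 7/28 (even weighting, day 7) | 0.125 | 0.707 | 11% |
| 10/28 (even weighting, day 10) | 0.179 | 1.010 | 17% |
| 0.50 | 0.250 | 1.414 | 29% |
| 0.75 | 0.375 | 2.121 | 56% |
| 1 (only post-discharge days count) | 0.500 | 2.828 | 80% |

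**What adjusting T2 for T0 could gain (illustration).** With T0–T2 correlation r and equal variances, the effective d is 0.50 / √(1 − r²), with one degree of freedom fewer. The correlations are assumed; the documents give none.

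| r | Effective d | Power, T2 adjusted for T0 | Power, unadjusted T2 t-test |
|---|---|---|---|
| 0.3 | 0.50/√0.91 = 0.524 | 84% | 80% |
| 0.5 | 0.50/√0.75 = 0.577 | 90% | 80% |
| 0.7 | 0.50/√0.51 = 0.700 | 98% | 80% |

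The T0 and T2 windows end 30 days apart and share no day, so a high correlation should not be presumed. At r = 0.1 the adjusted comparison still has 80.5% power, against 80.1% unadjusted.

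**The case against.** The strongest reply is that little hangs on this. It touches one of three outcomes at an interim visit, and the stated hypothesis makes no claim about early effect. A null at T1 would be ambiguous anyway, because so few calls have been made by then. All of that stands and limits the weight of the point. It does not remove the case for a caveat, since either cause makes a null T1 result weak evidence.

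A second reply is that the four-week period comes from a general description of the instrument. Item wording, the form used and how patients weight recalled days are not given. This also stands. A power range of 11% to 80% cannot size the problem, and its lower end assumes full effect from discharge, which sits badly with low early exposure.

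Three stronger readings are tempting, and the documents do not support them:

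- A reader might infer that 64 to 75% of the T1 effect is lost. Those are calendar shares, not measured losses.
- A reader might infer that section 2.9 treats every visit alike or pools T1 with T2. It does not say so. A GEE for change over time may well estimate visits separately, and the paired t-test most naturally compares T0 with T2, although it is within-group and does not settle the between-group visit. Nor does the plan explicitly propose a between-group change score, so there is no such method to object to.
- A reader might infer that the trial's quality-of-life result is biased or favours the intervention. The expected pull at T1 is toward zero, and T2 is untouched.

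**Conclusion.** The point holds as a minor one. On a literal four-week recall, most of what the SF-12 covers at T1 precedes the intervention, and none does at T2 if it is held on day 28. The T1 difference in PCS and MCS is expected to be attenuated by an amount the documents do not allow anyone to state, and this cannot be separated from low early exposure.

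The calendar shares rest on the stated visit times and recall period. The power figures are illustrative only: section 2.5 ties the effect size of 0.50 to no outcome or visit, and the correlations are assumed. The gap in the readable part of section 2.9 is that it names no visit for an unadjusted comparison and gives no model terms.

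**What to change.** In section 2.9:

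- Make T2 the main time point for between-group inference on PCS and MCS.
- In place of the unadjusted t-test, estimate the T2 difference adjusted for the T0 score, by ANCOVA or by a GEE on T1 and T2 with visit-specific group effects and T0 as covariate.
- Report the T1 SF-12 difference with its confidence interval as supportive. Add one sentence saying that most of a literal four-week window precedes discharge, so a null T1 result is not evidence of no early effect.
- Section 2.2 reports recruitment to January 2025. If outcomes have already been seen, disclose that T2 was named afterwards.

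State also whether T0 was completed before the patient knew the allocation. Sections 2.1 and 2.8 place both before discharge without giving their order, and adjustment works best if T0 came first.

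The cost is wording and a little analysis, with no new data and no change to the questionnaire. The downside is that there is no confirmatory early SF-12 result. If patients in practice answer for recent days, a real early effect would be reported as supportive only.

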2.9 Data analysis

Descriptive statistics of continuous variables are presented in mean and standard deviation (SD). Categorical variables are presented using frequencies and percentages. A Pearson's chi-square test or Fisher's exact test was used to analyze categorical variables, depending on whether the expected cell count was less than five. Continuous variables were compared using the independent t test. The paired t test was applied to compare the means

of the scores in each group before and after the interventions, and the independent t-test to compare the means of the scores in the two groups. To analyze the changes in cardiac symptom distress, self-care, and quality of life at different time points for the same study participant, the analysis was performed using the generalized estimating equations (GEE). An overall alpha-level of 0.05 was used as for statistical significance and all statistical tests were two-tailed. Statistical analyses were performed in SPSS versi

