2.3 Randomization

Eligible patients were provided with detailed information about the study and its objectives. Those who agree to participate were randomly assigned to the experimental group or the control group in a 1:1 ratio. The random numbers were generated by an independent person using a random number generator. Sealed envelopes were used to ensure allocation concealment. Due to the need for the experimental group to download and learn the electrocardiogram equipment, participant blinding was not feasible. However, the primary care physician and nurses are blinded to the allocation of the two groups.

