2.5 Sample size

The sample size was calculated using the effect size 0.50 from a similar study by Nobari et al. (2021), with G Power-3.1.9.2, the significance level at 0.05, and the power at 0.80, resulting in a minimum required sample size of 128 subjects. Considering potential attrition, an additional 20% subjects was included. Therefore, the total sample size was 160 patients, with 80 patients in the experimental group and 80 patients in the control group.

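### Make the between-group analysis adjust for the T0 score, and state the GEE terms; adjustment costs 1 degree of freedom per T0 term and is otherwise never less precise than the t-test or a change contrast

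*Combined protocol and SAP*

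**What the plan says.** Section 2.8 gives every outcome a pre-intervention value: "Outcomes were evaluated at three time points: two days before discharge (baseline, T0", followed by T1 at the first outpatient visit (7–10 days after discharge) and T2 at 4 weeks.

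Section 2.9 names three analyses of the scores:
- a paired t-test within each group, before against after;
- between groups, "the independent t-test to compare the means of the scores in the two groups";
- for changes over the time points, "the analysis was performed using the generalized estimating equations (GEE").

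No T0 covariate or change score is stated for the between-group t-test. No group, time, interaction or T0 term, contrast or working correlation is stated for the GEE. Nor does the section say which analysis carries the main conclusion. The available text of section 2.9 breaks off at the software version, but the sentence on the GEE is complete.

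On size, section 2.5 says "The sample size was calculated using the effect size 0.50 from a similar study", with alpha 0.05 and power 0.80, giving 128, raised to 160 for attrition. It does not say which outcome, visit or SD the 0.50 refers to.

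On timing, section 2.1 has patients "randomly assigned to either the experimental or control group before hospital discharge", and section 2.3 says "participant blinding was not feasible". Neither places randomisation before or after the T0 questionnaires.

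**The concern.** The trial pays for a T0 measurement of each score, yet the one between-group test that is fully described makes no stated use of it. The GEE may use T0, but how well depends on terms that are not written down. With free group, time and group-by-time terms, its T2 interaction is a difference in change from T0. If r is low, that contrast is less precise than the plain t-test. With T0 entered as a covariate, the group contrast is at least as precise as both.

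At stake is precision for all three outcomes. There is also ambiguity about what the reported GEE effect estimates, since the same data can give noticeably different power under choices that the plan leaves open.

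**Working it through.** **Inputs.** From the documents: effect size 0.50, alpha 0.05, power 0.80, N of 128 and then 160 (2.5); two-tailed tests (2.9); 1:1 allocation (2.3). Assumed: r, the T0-to-T2 correlation, over 0.1 to 0.7; equal SDs at T0 and T2; 0.50 in T2-score SDs unless stated otherwise.

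**1. The plan's own figures.** A two-sample t-test with noncentral t, d = 0.50, two-sided 0.05, needs 64 per group, which is 128 in total (power 0.801). With 20% attrition, 128/(1-0.20) = 160. Both stated figures reproduce as an unadjusted two-sided comparison.

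**2. Relative variance of the T2 group contrast** (t-test = 1):
- change from T0: 2(1-r)
- T0 as covariate: 1-r² = (1-r)(1+r)

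Since 1-r² ≤ 1 and 2(1-r) - (1-r²) = (1-r)² ≥ 0, the covariate form is never less precise than either alternative, apart from 1 degree of freedom. With unequal SDs s0 and s2, change variance minus covariate variance is (s0 - r·s2)², which is also never negative.

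**3. Power at 64 per group.** The standardised effect is 0.50/√(relative variance). Degrees of freedom are 126, or 125 with the covariate.

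| r | Variance, change | Variance, covariate | Power, t-test | Power, change | Power, covariate | SE reduction, covariate against t-test |
|---|---|---|---|---|---|---|
| 0.1 | 1.80 | 0.99 | 0.801 | 0.553 | 0.805 | 0.5% |
| 0.3 | 1.40 | 0.91 | 0.801 | 0.660 | 0.837 | 4.6% |
| 0.5 | 1.00 | 0.75 | 0.801 | 0.801 | 0.900 | 13.4% |
| 0.7 | 0.60 | 0.51 | 0.801 | 0.952 | 0.976 | 28.6% |

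The SE reduction is 1-√(1-r²). A simulation of 20,000 trials per setting gave covariate power of 0.836, 0.899 and 0.975 at r = 0.3, 0.5 and 0.7. At r = 0, allowing for chance T0 imbalance, covariate power is 0.798 against 0.801. That is the whole price of adjusting for a useless T0.

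**4. If 0.50 is in change-score SDs instead.** The T2-scale effect becomes 0.50·√(2(1-r)). Power for t-test / change / covariate is then 0.913/0.801/0.936 at r = 0.3 and 0.585/0.801/0.861 at r = 0.7. The levels move, but the ranking does not.

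**5. A GEE of T0, T1 and T2 with T0 means constrained equal.** The T2 estimate subtracts a × (T0 group difference), where a is the working T0–T2 correlation. Its relative variance is 1 - 2·a·r + a². An unstructured working correlation sets a = r and returns 1-r². An exchangeable one sets a near the average of the three pairwise correlations. With assumed T0–T1, T0–T2 and T1–T2 correlations of 0.5, 0.2 and 0.6, a = 1.3/3 = 0.433, and the variance is 1 - 2(0.433)(0.2) + 0.433² = 1.014. The covariate or unstructured form gives 1 - 0.2² = 0.960. The exchangeable version is then slightly worse than the t-test.

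**The case against.** **T0 is not simply unused.** A reader might infer that the plan throws the T0 score away. The text does not support that. Section 2.9 applies the GEE to changes across time points, section 2.8 makes T0 one of those points, and the paired t-test uses the before score within each arm. This stands. What remains is that the t-test has no stated T0 term, the paired test does not compare arms, and the GEE's use of T0 cannot be determined.

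**The gain may be small.** The documents give no r, and a low value is plausible for some scores. The SF-12, "a well-validated self-administered survey derived from the SF-36 questionnaire", covers the past four weeks, so T0 recall can span surgery while T2 recall covers the period at home. Self-care items on exercise and follow-up visits are asked of inpatients at T0. This also stands as a limit on the benefit over the t-test. It cuts the other way for an unconstrained GEE, which loses most at low r.

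**The t-test is valid.** A reader might infer bias or an underpowered trial. Randomisation makes the unadjusted comparison unbiased, and 128 and 160 are correct for it with 0.50 in T2 SDs.

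**T0 is called baseline.** A reader might infer that T0 answers were coloured by knowledge of the arm, since participants are unblinded and section 2.7 says "During hospitalization, the research team assisted in installing the ECG software". No section says that allocation was known at T0, and none shows that it was not. Any figure for the resulting bias would rest on an invented shift. Only the request to confirm the order survives.

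**Conclusion.** The point holds as an efficiency improvement and a specification gap. It is worth making, but it does not invalidate the plan. Adjusting for T0 is at least as precise as the t-test or a change contrast at every r, apart from 1 degree of freedom. That ranking needs near-equal arms, which the 1:1 design supports, and a T0 recorded before allocation was revealed. The size depends on r, which is assumed: power rises over the t-test by 0.004 at r = 0.1, 0.036 at 0.3, 0.099 at 0.5 and 0.175 at 0.7, with 0.50 in T2 SDs and equal SDs. The unstated GEE form can matter more. At r = 0.3, power is 0.660 if the model yields a change contrast and 0.837 if it adjusts for T0. Confidence in the ranking is high; confidence in the size of the gain is moderate at best.

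**What to change.** For each score, make the main between-group analysis one GEE or repeated-measures model of T1 and T2 with group, visit, group-by-visit, the T0 score and T0-by-visit. Report the group contrast at T1 and at T2, and state the working correlation. A GEE of T0, T1 and T2 with T0 means constrained equal is an acceptable equivalent only with an unstructured working correlation.

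State whether T0 was recorded before allocation was revealed. If it was not, keep the unadjusted T1 and T2 comparisons as the main analysis, give the adjusted model as a sensitivity analysis, and do not rest the conclusion on change from T0. A T0 difference caused by knowing the arm would pass in full into a change contrast and, with equal SDs, in proportion r into the adjusted one.

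The cost is SAP wording and 1 degree of freedom per T0 term, with no new data. Section 2.2 has recruitment ending in January 2025 and section 2.9 is in the past tense, so the outcome data may already have been analysed. If so, label the change post hoc and report the unadjusted comparison beside it. Stating the GEE terms that were used is needed in either case.

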2.6 The control group

Patients in the control group received standard care and were instructed by the ward nurses on nursing care, including wound assessment, education on diet, exercise, bathing, and medication, according to the post-coronary artery bypass surgery hygiene manual developed by the hospital. They were also instructed to monitor their blood pressure, blood glucose levels, and weight daily, and were scheduled for a follow-up phone call on the seventh day after discharge

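### Section 2.9 compares the groups with unadjusted t-tests and an unspecified GEE; one model of T1 and T2 adjusted for T0 would be more precise, and would limit bias from some patterns of loss

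*Combined protocol and SAP*

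**What the plan says.** Section 2.5 derives 128 patients from an effect size of 0.50, alpha 0.05 and power 0.80, then goes to 160: "Considering potential attrition, an additional 20% subjects was included".

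Section 2.8 sets three assessments: T0 "two days before discharge (baseline, T0"), T1 "at the first outpatient visit (7–10 days post-discharge, T1") and T2 at four weeks. Section 2.1 has patients "randomly assigned to either the experimental or control group before hospital discharge", and neither section says whether T0 was answered before or after allocation was known.

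Section 2.9 uses paired t-tests within groups and "the independent t-test to compare the means of the scores in the two groups". A further analysis of the repeated scores has this stated purpose: "To analyze the changes in cardiac symptom distress, self-care, and quality of life at different time points for the same study participant". The only method named for that purpose is a GEE, in a single clause: "the analysis was performed using the generalized estimating equations (GEE"). The visible text does not give the GEE's terms, its working correlation, the role of T0, the visit of main interest, or whether the t-test or the GEE carries the between-group result. It breaks off at the software version.

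Contact differs by arm. Controls were "scheduled for a follow-up phone call on the seventh day after discharge" (section 2.6). Section 2.7 adds a call every three days for four weeks in the telehealth arm, about nine calls (28/3 = 9.3).

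**The concern.** Two things are left open. First, a t-test on T2 scores ignores T0, which is collected anyway, and ignores the T1 scores of patients lost before T2. Both carry information about T2, so precision is given away even if loss is purely random.

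Second, naming a GEE does not fix how it treats incomplete patients. Under an independence correlation it behaves much like the t-test at T2; under an unstructured one it uses T1 to inform T2. If loss is related to the score and differs by arm, that choice decides how much bias remains. Heavier loss of the worst-off patients among controls would hide a benefit; heavier loss of them in the telehealth arm would create one.

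**Working it through.** **The plan's own figures.** A two-sided two-sample t-test with d = 0.50 and alpha 0.05 needs 64 per arm (power 0.801), so 128. Then 128/(1 − 0.20) = 160. Both reproduce; the allowance is 160 − 128 = 32 patients.

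**Assumed inputs (the documents give none).** Scores have SD 1 and correlations T0–T1 0.4, T1–T2 0.6 and T0–T2 0.3; 80 per arm. Simulations used 20,000 trials per scenario (Monte Carlo error about 0.0015 SD for bias, 0.002 for type I error, 0.003 for power).

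**Precision: 20% random loss at T2, so 64 of 80 per arm remain.**
- t-test: √(2/64) = 0.177.
- T0 adjustment, completers only: 0.177 × √(1 − 0.3²) = 0.169.
- T0 adjustment with T1 also used: the T1–T2 correlation given T0 is (0.6 − 0.4 × 0.3)/√(0.84 × 0.91) = 0.549, so the variance of T2 given T0 and T1 is 0.91 × (1 − 0.549²) = 0.636. SE = √(2 × [(0.91 − 0.636)/80 + 0.636/64]) = 0.164 in large samples; simulated 0.165.
- GEE change-from-T0 contrast without T0 adjustment: √(2 × [1/64 + 1/80 − 2 × 0.3/80]) = 0.203 under independence, and √(2 × [1.4/80 + 0.636 × (1/64 − 1/80)]) = 0.197 unstructured; simulated 0.202 and 0.196.

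Simulated power at 0.50 SD is 0.801 (t-test), 0.834 (T0 adjustment of completers), 0.855 (mixed model with T0), 0.865 (unstructured GEE with T0) and 0.700–0.724 (unadjusted GEE contrast). About two-thirds of the gain is T0 adjustment: (0.177 − 0.169)/(0.177 − 0.165) = 0.67.

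Over T0 correlations of 0 to 0.5, power is 0.83–0.91 for the mixed model, 0.80 for the t-test and 0.57–0.84 for the unadjusted GEE contrast. Under independence that contrast matches the t-test when 1/80 = 2r/80, that is r = 0.5; unstructured, a little lower. With all correlations at 0.7, the SEs are 0.127 (adjusted model), 0.135–0.147 (unadjusted GEE, exchangeable and independence) and 0.181 (t-test).

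**Bias: no true effect, loss of 25% in controls and 15% in telehealth (20 + 12 = 32 patients), logit slope 1 per SD in both arms.** Entries are absolute bias in SD / type I error.

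| Loss | t-test | GEE indep. | GEE exch. | GEE unstr. | GEE unstr. + T0 | Mixed + T0 |
|---|---|---|---|---|---|---|
| A: T2 lost by observed T1 | 0.050/0.059 | 0.049/0.062 | 0.017/0.056 | 0.003/0.054 | 0.004/0.055 | 0.002/0.049 |
| B: T1 lost by unseen T1 | 0.081/0.076 | 0.081/0.072 | 0.058/0.062 | 0.049/0.059 | 0.048/0.067 | 0.050/0.061 |
| C: T2 lost by unseen T2 | 0.082/0.075 | 0.082/0.073 | 0.061/0.063 | 0.054/0.061 | 0.055/0.064 | 0.055/0.058 |

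A check on size: in A the selection acts through T1, so the t-test bias should be the C figure times the T1–T2 correlation, 0.082 × 0.6 = 0.049, as found.

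The two unstructured GEE columns show where the reduction comes from. Adding T0 leaves the bias unchanged (0.003 v 0.004, 0.049 v 0.048, 0.054 v 0.055); using T1 with a suitable correlation does the work.

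Milder inputs give less. At slope 0.5 the t-test bias is 0.03 (A), 0.045 (B) and 0.05 (C); with 22.5% v 17.5% it is 0.02 (A) and 0.04 (B). Random loss, or the same mechanism at 20% in both arms, gives no bias for any method (type I error 0.049–0.058).

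**The case against.** The strongest reply is that the harm is small and every loss input is assumed. This stands. In A, the only situation the model resolves, t-test bias is 0.05 SD: a tenth of the design effect (0.05/0.50), 0.28 of the standard error (0.05/0.177), with type I error 0.059. If the planned GEE were exchangeable, bias would already be 0.017. In B and C the adjusted model gains only 0.006–0.010 SD over exchangeable.

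The t-test also meets the plan's 80% power target with 20% loss, so the precision gain is an efficiency gain and does not repair a shortfall. That stands too.

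Four stronger readings are tempting, and the documents do not support them.
- That the plan has no missing-data method: section 2.9 is cut off, so this cannot be shown.
- That loss will differ by arm: unequal contact makes it conceivable, but no rate, mechanism or direction is given, and section 2.5 gives no rate for a missed T1. Attending follow-up is among the activities behind the self-care scale, but that applies to both arms alike. The larger biases of 0.10–0.17 SD for the t-test need score-related loss in controls only, which no section supports.
- That T0 adjustment removes bias: the table shows otherwise.
- That the GEE leaves the trial at about 70% power: this needs a change-from-T0 contrast, which section 2.9 does not state, and a T0–T2 correlation near 0.3. From about 0.5 upward that contrast is at least as precise as the t-test.

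**Conclusion.** The point holds as a modest improvement worth making. It does not invalidate the planned analysis.

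The firm part is precision. With 20% random loss and a T0–T2 correlation of 0.3, the adjusted model lowers the SE by about 7% (0.165 against 0.177), and power goes from 0.80 to about 0.85. It is more precise than the unadjusted GEE contrast at every correlation tried.

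The bias part is conditional on loss that is score-related and differs by arm. About 0.05 SD falls to about 0 if loss depends on the observed T1 score; about 0.08 falls only to about 0.055 if it depends on the unseen T2 score. The correlations, loss rates and slopes are assumptions, so confidence is medium.

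**What to change.** 1. For each outcome (CSS, self-care, SF-12 PCS and MCS), make the between-group difference at T2 the main contrast. Estimate it in all randomised patients as allocated from one model of the T1 and T2 scores with group, visit, group-by-visit, T0 and T0-by-visit. A mixed model with unstructured covariance is preferable. If the planned GEE is kept, use an unstructured working correlation with a small-sample standard-error correction: with T0 its type I error ran slightly above the mixed model's (0.055 v 0.049 in A), so part of its power of 0.865 may be flattering.
2. Keep the t-tests as descriptive.
3. State whether T0 was answered before allocation was known. If it was not, T0 itself could be influenced by group, and adjusting for it needs more care.
4. Report missing scores by arm and visit, with reasons. Unless the cut-off text already has a sensitivity analysis, add a short one: impute by arm from all three visits, then shift imputed scores in the unfavourable direction by, for illustration, 0.3 and 0.6 SD, in controls only, in telehealth only and in both. At 25% loss, 0.6 SD in controls only moves the estimate by 0.6 × 0.25 = 0.15 SD.

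The cost is plan wording and a little more analysis; T0 is already collected. Section 2.2 puts the end of recruitment at January 2025, so if outcome data have already been seen by arm, the model must be reported as chosen after the fact.
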